8.1. Primary Efficacy Endpoint

As described in section 3.2.1, the primary efficacy endpoint is the ratio of coughs per hour in the 24 hours following administration of study drug. The cough counts will be provided based on the VitaloJAK recordings, following evaluation by the cough analysis technicians. This ratio of the cough count observed at Visit 4, Visit 5, and Visit 6 to the cough count observed at baseline will be transformed using the common logarithm for the purposes of analysis. The last planned cough recording prior to the first dose of study drug should occur at Visit 2, however, if the cough count at Visit 2 is missing, then according to the general conventions for baseline, the cough count from Visit 1 will be used as the baseline. As well, in some instances, the cough recording at Visit 2 may span Visit 3 and include time

Shionogi 1812VA323

after the first dose of study drug. If the end date and time of the Visit 2 cough recording is after the date and time of the first dose of study drug, then the cough count from Visit 1 will be used as the baseline.

8.1.1. Primary Analysis

The null hypotheses of equality between the treatment and placebo effects will be tested using a mixed model, containing treatment group, week (as a classification term), and the interaction between treatment group and week as fixed effects; patient as random effect; and region and the common logarithm of the frequency of coughs per hour at baseline as covariates. In this model, the covariance structure will be given as unstructured, and the degrees of freedom will be derived using the Kenward-Roger method. Should the model fail to converge using the unstructured covariance, compound symmetry will be used. Using this model, the log-transformed ratio of the number of coughs per hour in 24 hours after 4 weeks of administration of study drug will be used to evaluate the null hypothesis at each dose level of S-600918 at the 2-sided alpha level of 0.05 among the FAS.

The primary analysis will summarize each of these three 2-way comparisons, presenting the estimate for the difference of the effects of treatment at Visit 6, the 95% confidence interval for this difference, and the p-value based on the hypothesis and model described above. Furthermore, the time course of the treatment effect for each treatment group will be plotted with the mean and 95% confidence interval.

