9.10.3.1 Analysis of Primary Endpoint

A mixed effect model will be applied to the common logarithm of the ratio of the number of coughs per hour in 24 hours at Visit 4, Visit 5, and Visit 6 to that at baseline as response. This model will contain treatment group, week, and the interaction between treatment group and week as fixed effect; patient as random effect; and region and the common logarithm of the frequency of coughs per hour in 24 hours at baseline as covariates. The covariance structure will be determined to be unstructured. When the mixed model with unstructured covariance fails in convergence, compound symmetry will be applied as covariance structure. Under this model, the ratio of the number of coughs per hour in 24 hours after 4 weeks of administration to that at baseline will be compared between each dose level of S-600918 and placebo. The dose-response relationship will be evaluated by a comparison of each dose level of S-600918 to placebo. This analysis will be performed for the FAS and the PPS.

Summary statistics for the number of coughs at each visit will include the geometric mean and its 95% confidence interval.

A subgroup analysis based on the combination of region and cough count at baseline will be performed and will include the following subgroups: region (Japan, Europe, and the United States) and cough count at baseline (\geq 30 coughs/hour and <30 coughs/hour). Another subgroup analysis based on the combination of region and cough count at screening (Visit 1) will be performed and will include the following subgroups: region (Japan, Europe, and the United States) and cough count at screening (\geq 30 coughs/hour or <30 coughs/hour).

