4.1. Sample Size

The sample size has been determined using the results of the VA322 proof-of-concept study. In that VA322 study, the mean (\pm SD) of the common log-transformed ratio of cough frequencies per hour in 24 hours after 2 weeks of treatment to that at baseline was -0.327 (0.379) in the S-600918 150-mg treatment (N = 31) and -0.160 (0.363) in the placebo treatment (N = 30). The difference in the common log-transformed ratio of the cough frequencies per hour in 24 hours after 4 weeks of treatment to that at baseline between each S-600918 dose group and placebo and the standard deviation (SD) in each treatment group in the Phase 2b study were assumed to be the same as those after 2 weeks of treatment observed in the proof-of-concept study, and -0.163 and 0.371, respectively. As a result, the effect size, ie, the difference divided by the SD, was determined to be -0.44. Based on this assumption, the sample size required to assure 80% power with a 2-sided 5% level of significance was calculated to be 83 patients per treatment group. Allowing for exclusion of 10% of patients per treatment group, 93 patients per treatment group will be needed. Therefore, the planned sample size at randomization was determined to be a total of 372 patients.

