8.1.4. Other Analyses of the Primary Endpoint

Summary statistics for the average number of coughs per hour in 24 hours at each visit will be presented by treatment group using the geometric mean and its 95% confidence interval for the FAS.

Subgroup analyses will be performed to evaluate the primary efficacy endpoint among subgroups of patients for the FAS. For these subgroup analyses, the primary analysis method mentioned in the section 8.1.1 will be repeated. Within this framework, the subgroups below will be analyzed:

- 1. Region (1-1: Japan, Europe, United States, 1-2: Japan, Europe and United States)
- 2. Hourly cough count at baseline (≥30 coughs/hour, <30 coughs/hour)
- 3. Cough count at Visit 1 (≥30 coughs/hour, <30 coughs/hour)
- 4. Pulmonary/Cough History (Asthma, Cough variant asthma [CVA], Gastroesophageal reflux disease [GERD], Upper airway cough syndrome including postnasal drip, rhinosinusitis, and rhinitis [UACS], Eosinophilic bronchitis including atopic cough [EB], Sinobronchial syndrome [SBS], Unexplained cough, Other, and Refractory cough, i.e., other than Unexplained cough and Other). A patient may have more than one pulmonary history. Such patients will be included in each category by pulmonary history.

A forest plot will also be provided based on the estimates for the difference of the effects of treatment at Visit 6 and its 95% Confidence Interval for the subgroups above.

The primary analysis framework will be used to assess characteristics of the dose-response relationship on the primary efficacy endpoint. The framework will be applied as originally described as well as to the log-transformed ratio of average coughs per hour in 24 hours following 4 weeks of treatment to that at baseline. The below comparisons will be presented for each of these models.

- Placebo versus 50 mg, 150 mg, and 300 mg S-600918
- Placebo and 50 mg S-600918 versus 150 mg and 300 mg S-600918
- Placebo, 50 mg, and 150 mg S-600918 versus 300 mg S-600918
- Linear Trend Test across all Treatment Groups

This framework above will be applied to the log-transformed ratio of average coughs per hour in 24 hours following 3 weeks of treatment to that at baseline, as well.

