8.2.3. Analysis of Cough Severity (VAS)

The change in weekly cough severity at Visit 4, Visit 5, and Visit 6 to that at baseline will be analyzed using the primary analysis framework for the FAS. Similarly, the change in daily cough severity from Day 1 through Day 7 will be analyzed using the primary analysis framework for the FAS, only using Day 7 in place of Visit 6.

Both weekly and daily cough severity will also be summarized using descriptive statistics at each planned assessment by treatment group for the FAS.

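### The only covariance fallback, compound symmetry, pools variance over visits although the test is at the last visit; a fallback that keeps visit-specific variances is a cheap improvement

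*SAP*

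**What the plan says.** SAP 8.1.1 models the log10 ratio to baseline at Visits 4, 5 and 6, with treatment, week and their interaction as fixed effects and region and log baseline as covariates. It also lists "patient as random effect", specifies an unstructured covariance with Kenward-Roger degrees of freedom, and reports each dose-placebo difference at Visit 6. On non-convergence: "Should the model fail to converge using the unstructured covariance, compound symmetry will be used". Protocol 9.10.3.1 has the same rule: "When the mixed model with unstructured covariance fails in convergence, compound symmetry will be applied as covariance structure". Neither document names an intermediate structure or an empirical standard error.

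The framework is reused widely:
- Daily diary VAS over Days 1 to 7 (SAP 8.2.3), "only using Day 7 in place of Visit 6".
- Subgroups by region, cough count and cough history (SAP 8.1.4): "For these subgroup analyses, the primary analysis method mentioned in the section 8.1.1 will be repeated".
- Awake and asleep counts, weekly VAS and LCQ (SAP 8.2.1, 8.2.3, 8.2.4).

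ICIQ-SF and SF-36 have one post-baseline visit, so the question does not arise for them.

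**The concern.** A fallback should protect the inference when the preferred model fails. This one removes the feature that a single-visit test depends on, a variance estimated for that visit. Under compound symmetry the Visit 6 standard error comes from the average of the visit variances. If Visit 6 is the most variable visit, its confidence interval is too narrow and the stated 5% level is exceeded. Kenward-Roger does not repair this, because it works within the assumed structure. Testing is not adjusted for multiplicity (SAP section 4), so no margin absorbs the excess.

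The wording of the main model also needs attention. Read literally, a random patient effect plus an unstructured within-patient matrix has one more covariance parameter than the data can identify.

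**Working it through.** **Inputs.** From SAP 4.1: difference and SD "observed in the proof-of-concept study, and -0.163 and 0.371, respectively", and "the effect size, ie, the difference divided by the SD, was determined to be -0.44". The SD comes from one time point, two weeks in the proof-of-concept study, and is carried over to week 4. SDs at Visits 4 and 5 are not given, so any pattern over visits is an assumption and is shown as a range.

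**1. Planned sample size.** The plan states that "the sample size required to assure 80% power with a 2-sided 5% level of significance was calculated to be 83 patients per treatment group". The normal approximation gives 2 × (1.960 + 0.842)² × (0.371/0.163)² = 81.3, rounded up to 82. The noncentral t calculation gives 83, with power 0.803. Then 83/0.9 = 92.2, rounded up to 93, and 4 × 93 = 372. The plan's figures reproduce.

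**2. Effect of pooling.** With complete data the Visit 6 contrast is the same under both structures, apart from the small covariate adjustment. Only its standard error changes. Write s4, s5, s6 for the SDs at Visits 4, 5 and 6:

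- ratio = SE(compound symmetry) / true SE = √[(s4² + s5² + s6²)/3] / s6
- true two-sided alpha = 2 × [1 − Φ(1.96 × ratio)]
- true SE at 83 per group = 0.371 × √(2/83) = 0.0576

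Fix s6 = 0.371 and let the SD change linearly over weeks 1, 3 and 4, so that s5 = s4 + (2/3)(s6 − s4). For a 1.2-fold rise, the mean variance is (0.0956 + 0.1228 + 0.1376)/3 = 0.1187, its root is 0.3445, and the ratio is 0.3445/0.371 = 0.929.

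| s6/s4 | s4 / s5 / s6 | Ratio | SE used | True alpha |
|---|---|---|---|---|
| 0.9 | 0.412 / 0.385 / 0.371 | 1.050 | 0.0605 | 4.0% |
| 1.0 | 0.371 / 0.371 / 0.371 | 1.000 | 0.0576 | 5.0% |
| 1.1 | 0.337 / 0.360 / 0.371 | 0.960 | 0.0553 | 6.0% |
| 1.2 | 0.309 / 0.350 / 0.371 | 0.929 | 0.0535 | 6.9% |
| 1.5 | 0.247 / 0.330 / 0.371 | 0.863 | 0.0497 | 9.1% |

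Coverage of the 95% interval is 100% minus the alpha shown.

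**3. Simulation check.** REML fits of both structures under no treatment effect: four arms of 93, region and baseline covariates, about 10% monotone dropout, correlation 0.6 (assumed), 400 runs per scenario.

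| s6/s4 | Mean SE, compound symmetry vs unstructured | Rejection, compound symmetry vs unstructured |
|---|---|---|
| 1.0 | 0.0563 vs 0.0563 | 0.033 vs 0.035 |
| 1.2 | 0.0521 vs 0.0562 | 0.058 vs 0.035 |
| 1.5 | 0.0482 vs 0.0562 | 0.083 vs 0.033 |

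Monte Carlo error is about 0.01, so the contrast between the structures matters more than the absolute levels. The SE ratios, 0.0521/0.0562 = 0.927 and 0.0482/0.0562 = 0.858, agree with step 2.

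**4. Covariance parameters.**

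| Structure | 3 visits | 7 days |
|---|---|---|
| Unstructured | 6 | 28 |
| Heterogeneous Toeplitz | 5 | 13 |
| Heterogeneous compound symmetry | 4 | 8 |
| Compound symmetry | 2 | 2 |

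A separate random patient effect adds one parameter and identifies nothing new: 7 for 6 quantities in the main three-visit model, and 3 for 2 in the fallback.

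**The case against.** The strongest objection is that the fallback will hardly ever be used. Six covariance parameters with three visits and about 372 patients should fit without trouble. In a separate REML check (correlation 0.6, about 5% dropout plus 3% intermittent missing values), the unstructured model at 83 per arm converged in 300 of 300 runs for three visits and in 200 of 200 for the seven-day diary. With 8 and 5 patients per arm it converged in 200 of 200 and 199 of 200. Those were Gaussian data in purpose-written code, not SAS, so they do not settle real subgroups whose sizes are not stated. For the primary FAS analysis the objection stands.

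Three stronger readings are tempting, and the documents support none of them:

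- A reader might infer that the random patient effect will itself make the model fail and trigger the fallback. The text can equally mean that patient is the subject of the repeated measures. A literal fit with a generalised inverse converged in 100 of 100 runs and matched the plain unstructured fit to within 1e-5. The wording is redundant, but it has not been shown to cause failure.
- A reader might infer that variance of change from baseline must grow with time. The plan has an SD at one time point and assumes the same value at week 4. Steep rises in the diary SD within a week would be invented inputs.
- A reader might infer that the primary test does not hold 5%. That needs both non-convergence and rising variance.

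The ANCOVA sensitivity analyses in SAP 8.1.2 do not pool variance over visits, which is some protection. However, the two versions clearly planned impute by last observation or baseline, and they cover the primary endpoint in the FAS and PPS, not the diary or the subgroups. The fallback is also pre-specified and consistent across documents, so this is a choice that can be bettered and not a contradiction.

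**Conclusion.** The point holds as a conditional weakness: if the fallback is used and the SD rises over visits, the final-visit standard error is too small. For an assumed 1.1- to 1.5-fold rise it is 4% to 14% too small, and true alpha is about 6% to 9%. There is no error if the SD is flat, and the test is conservative if it falls (4.0% at 0.9-fold). These figures take a Visit 6 SD of 0.371, a linear change in SD and complete data.

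The primary FAS conclusion is not in doubt on this account. The cases to protect are the small cough-history subgroups and possibly the seven-day diary model with its 28 covariance parameters. This is a cheap improvement.

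**What to change.** In the SAP, before unblinding:

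1. In 8.1.1, state that patient is the subject of the unstructured repeated covariance, and delete the separate random patient effect.
2. Replace the single fallback with an ordered list: heterogeneous Toeplitz, then heterogeneous compound symmetry, both with Kenward-Roger. Keep compound symmetry only as the last resort, with an empirical (sandwich) standard error and a compatible degrees-of-freedom method.
3. Apply the list wherever the framework is reused, including 8.1.4 and 8.2.3, and record the departure from protocol 9.10.3.1 in SAP section 13, which now reports no changes.

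The cost is a few SAP sentences and a few more variance parameters in the fallback. Recording the change in section 13 avoids a protocol amendment. For three visits, heterogeneous Toeplitz saves only one parameter and equates the Visit 4-5 and Visit 5-6 correlations despite gaps of 14 and 5 days. The second step and the terminal option are therefore needed. The sandwich standard error can itself be too small in very small subgroups, so its use there should be flagged in the output.

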8.1.2. Sensitivity Analyses of the Primary Endpoint

A sensitivity analysis of the primary efficacy endpoint will be performed on the FAS using an analysis of covariance containing treatment group, as factor; and region and the common logarithm of the frequency of coughs per hour at baseline as covariates. It is expected that this ANCOVA will perform similarly as the primary analysis, using the observed data. Thus, two sensitivity analyses using this ANCOVA model on the FAS will be performed: one that imputes missing observations with the last post-baseline observation, and that imputes the baseline cough counts per hour for missing observations.

Furthermore, the primary analysis will be repeated for the FAS using 1) the protocol visit windows found in Table 7-2 of the Protocol, and 2) the nominal visit analysis windows presented below in Table 8-1.

Visit	Target Day	Window Start Day	Window End Day
Visit 1	-18	-28	-18
Visit 2	-1	-1	-1
Visit 3	1	1	1
Visit 4	8	2	14
Visit 5	22	15	24
Visit 6	27	25	Latest of Day 28, Day of Visit 6, and Day of Last Dose of Study Drug

Table 8-1: Analysis Visit Windows for Sensitivity Analysis

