7.4.1 Number of Coughs (VitaloJAK™ Cough Monitor)

The number of coughs over a 24-hour period will be recorded at Visit 1, Visit 2, Visit 4, Visit 5, and Visit 6 with the VitaloJAKTM cough monitor [27]. This cough monitor has CE marking in the European Union and 510(k) approval from the United States Food and Drug Administration (FDA).

The cough monitor will be applied to the patient at each of these visits, and the patient will be instructed to remove the monitor after 24 hours. Instructions for the application of the cough monitor to the patient are specified in a separate document.

If, based on initial assessment at the study site, the cough count recording at Visit 1 or Visit 2 is considered to have failed for any reason, the recording may be repeated (see details for Visit 1 in Section 8.1 and for Visit 2 in Section 8.3). Repeat recording of the cough count is not permitted at any other visits in the study.

Data collected with the cough monitor will be sent from the study site to the cough monitor analysis institution via the web portal of that institution. The number of coughs will be measured (including classification of awake and asleep hours) by cough analysis technicians for each of the following periods:

- 24 hours
- Waking hours
- Sleeping hours

The number of coughs will be reported by the cough monitor analysis institution to the sponsor, with counts provided for each 24-hour period and for the waking hours and the sleeping hours within each 24-hour period. Procedures regarding the cough monitor analysis are specified in a separate document.

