- Blood chemistry (ALP, ALT, AST, total bilirubin, GGT, lactate dehydrogenase, blood urea nitrogen, creatinine, sodium, potassium, chloride, calcium, glucose, total protein, uric acid, total cholesterol, and creatine phosphokinase).
- Urinalysis (glucose, occult blood, protein, and urobilinogen).
- Urine pregnancy test for women not identified to be postmenopausal (defined as at least 12 months of spontaneous amenorrhea in women >45 years of age) or surgically sterile by hysterectomy, bilateral oophorectomy, and/or bilateral salpingectomy or tubal ligation (Section 7.6.2.2).

Note: Record on the appropriate eCRF page, as specified in Section 7.6.2.1 and Section 7.6.2.2.

- Obtain an ECG after the patient has been in a recumbent or semi-recumbent position for approximately 3 minutes. Record on the appropriate eCRF page, as specified in Section 7.6.4.
- Record adverse events (Section 7.6.5).
- If, at any time during the study, the patient had a taste-related adverse event after initiation of study treatment, have the patient complete on the electronic tablet the taste questionnaire.
- If applicable, collect the cough monitor from the patient and assess whether the device operated without malfunction and whether the patient used it properly.
- Collect the study drug wallet and assess patient compliance with study drug administration (Section 5.9). Record the number of tablets of study drug taken daily and the date taken on the appropriate eCRF page, as well as the number of tablets returned and the date of return.
- Confirm that the patient has entered in the study drug wallet the date and time of study drug administration for (as applicable) the day of Visit 3, Visit 4, and Visit 6. **Note:** For Visit 4 and Visit 6, an entry of the date and time of study drug administration is required for the day before the visit and the day of the visit. Record the date and time of study drug administration for (as applicable) the day of Visit 3, Visit 4, and Visit 6 on the appropriate eCRF page.
- If applicable, collect the eDiary from the patient.
- If applicable, upload the cough monitor recording to the specified site within 1 business day after receipt of the cough monitor.

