Average daily number of coughs per hour; at								
Visit 2, assess pt vs Exclusion Criterion #1 [g]								
Daily severity of cough (VAS); at Visit 1 and								
Visit 2, assess pt vs Inclusion Criterion #5 [h]	•		-	1				
Instruct pt on use of cough monitor and apply monitor	X	X [i]		X [j]	X [j]	X [j]		

Confidential Page 96 of 110

	Screenin	g Period	Tr	eatment Peri	od (Day 1 to 2	8)	Follow-u	p Period
							Early	
							Discontinu-	
							ation Visit	
		Visit 2					(if study	
		(Second					drug is	
		screening					discontin-	
	Visit 1	≥17 days					ued prior to	
	(First	after					1 day after	(End-of-
Visit	screening)	Visit 1)	Visit 3	Visit 4	Visit 5	Visit 6	Visit 6) [a]	study Visit)
Week	_	_	_	1	3	4	_	_
Day	Day -28 to -18	Day -1	Day 1	Day 8	Day 22	Day 27 [b]	_	Day 42
Study Visit	Day -28 to -18	Day -1	Day 1 (the day after Day -1)	1 week after Visit 3	3 weeks after Visit 3	2 days prior to 4 weeks after Visit 3	Day of last dose of study drug	2 weeks after last dose of study drug
Allowable time window (days)	_	0	0	± 2	± 2	- 2	+ 3	+ 7
Receive cough monitor from pt and assess its use [k]	X [1]		X [m]		X	X	X [n]	X
Upload cough monitor recording within 1 business day after receipt of cough monitor	X		X		X	X	X [n]	X
Clinical assessments								
Perform physical examination	X [o]	X [p]	X [p]	X [p]		X [p]	X [p]	X [p]
Measure blood pressure and pulse rate [q]	X	X	X	X	X	X	X	X
Record adverse events	X	X	X	X	X	X	X [r]	X
Administer taste questionnaire [s]						X [s]	X [s]	
Laboratory assessments								
Obtain blood and urine samples for routine laboratory tests; if applicable, report liver chemistry abnormalities (Appendix 2) on appropriate page of eCRF [t, u]	X	X		X		X	X	Х

Confidential Page 97 of 110

	Screenin	g Period	Tr	eatment Peri	od (Day 1 to 2	8)	Follow-u	p Period
							Early Discontinuation Visit	
		Visit 2					(if study	
		(Second screening					drug is discontin-	
	Visit 1	≥17 days					ued prior to	Visit 7
	(First	after					1 day after	(End-of-
Visit	screening)	Visit 1)	Visit 3	Visit 4	Visit 5	Visit 6	Visit 6) [a]	study Visit)
Week	_		_	1	3	4	_	_
Day	Day -28 to -18	Day -1	Day 1	Day 8	Day 22	Day 27 [b]	_	Day 42
Study Visit	Day -28 to -18	Day -1	Day 1 (the day after Day -1)	1 week after Visit 3	3 weeks after Visit 3	2 days prior to 4 weeks after Visit 3	Day of last dose of study drug	2 weeks after last dose of study drug
Allowable time window (days)	_	0	0	± 2	± 2	-2	+ 3	+ 7

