4.3.2. Full Analysis Set (FAS)

The FAS will include all randomized patients who receive at least 1 dose of study drug and who have accepted cough monitor assessment at both baseline and at least 1 visit after initiation of study drug. Presentations based on this set of patients will group them according to their randomized treatment. The primary efficacy analysis will be performed on the full analysis set as well as the per protocol set (below). The primary hypothesis will be tested using the FAS. Patients in the all randomized population who fail to meet these criteria for entry in to the FAS will be listed with their reason(s) for exclusion from the FAS.

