4.3.3. Per Protocol Set (PPS)

The PPS will include all randomized patients who are included in the FAS, provided they:

- Meet all inclusion criteria affecting the evaluation of efficacy
- Meet no exclusion criteria affecting the evaluation of efficacy
- Do not have any major protocol deviations affecting the evaluation of efficacy (as defined in the Study Deviation Rules Document)
- Do not use any prohibited therapy affecting the evaluation of efficacy during the study

The criteria above represent an adherence to the specifications of the protocol with regards to efficacy assessments. The details of the rules used to make the determination of which criteria affect the evaluation of efficacy will be provided in a separate document that will be reviewed by study personnel at the sponsor. The first version of this Study Deviation Rules Document will be completed and signed off prior to the first patient being randomized. This document will be finalized prior to unblinding. Patients who receive any dose of the incorrect study drug will not be included in the PPS. Prohibited therapies will be assessed by a medical review to determine whether they affect the evaluation of efficacy. This review will be finalized prior to final unblinding.

Presentations based on this set of patients will group them according to their randomized treatment. Supplementary analyses will be performed on the PPS. Patients in the FAS who fail to meet these criteria for entry in to the PPS will be listed with their reason(s) for exclusion from the PPS.

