5.1. Disposition

Among patients randomized, the number and percentage of patients who complete the study and who withdraw from the study, as well as the reasons leading to withdrawal, will be summarized by treatment group. Also, among all randomized patients, the number of patients included in each analysis population defined in section 4.3 will be summarized by treatment group, as well as overall. As well as randomized patients, patients withdrawn from the study during screening period will be tabulated by reason of withdrawal and listed.

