8.1.3. Supplementary Analyses of the Primary Endpoint

The Primary Analysis described in section 8.1.1 and the Sensitivity Analyses described in section 8.1.2 will be repeated on the PPS as supplementary analyses.

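### The baseline-value sensitivity analysis is confined to the FAS, so it leaves out dosed patients with a baseline but no accepted post-dose recording, whom it alone could include

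*SAP*

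**What the plan says.** SAP 8.1.2 plans two imputation analyses of the primary endpoint by ANCOVA, one using the last post-baseline value and one using the baseline value. Both use the FAS: "two sensitivity analyses using this ANCOVA model on the FAS will be performed". The remaining sensitivity analyses in that section only change visit windows. SAP section 4 otherwise rules out imputation in principle.

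SAP 4.3.2 limits the FAS to randomised, dosed patients "who have accepted cough monitor assessment at both baseline and at least 1 visit after initiation of study drug". Protocol 9.3 has the same structure. SAP 8.1.3 says that the primary and sensitivity analyses "will be repeated on the PPS as supplementary analyses", but SAP 4.3.3 makes the PPS a subset of the FAS: "The PPS will include all randomized patients who are included in the FAS".

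Protocol 7.4.1 fixes the recording visits: "The number of coughs over a 24-hour period will be recorded at Visit 1, Visit 2, Visit 4, Visit 5, and Visit 6". The first after dosing is Visit 4 (Day 8, window Day 6 to 10), and a failed post-dose recording may not be repeated. In Protocol Appendix 1, the row "Instruct pt on use of cough monitor and apply monitor" has no entry for the Early Discontinuation Visit or Visit 7. Protocol 8.8 provides only for return of a monitor already issued: "If applicable, collect the cough monitor from the patient". Under SAP Appendix 2 a rejected count is missing.

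On reporting, SAP 5.1 states that "the number of patients included in each analysis population defined in section 4.3 will be summarized by treatment group", and SAP 4.3.2 adds a listing of patients outside the FAS with reasons.

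**The concern.** A baseline-value analysis asks whether the result survives if patients with missing data are credited with no benefit. The patients with the least follow-up are those who took study drug and left before any post-dose recording. Last-value imputation has nothing to carry forward for them, and the mixed model has no response to fit. Baseline-value imputation could include them, and only the choice of population keeps them out.

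The omission matters most if early loss differs between arms. The objective is dose selection, so if one dose loses more patients in the first week than another, the two comparisons with placebo could shift by different amounts and no planned analysis would show it. Tables of counts and of adverse events leading to discontinuation would show that loss occurred, but give no corresponding treatment difference with a confidence interval.

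**Working it through.** **Who is left out.** A patient with a baseline but no accepted post-dose recording fails the FAS rule, and so the PPS rule. This covers patients who stop before a Visit 4 recording and patients whose post-dose recordings are all missing or rejected. Two groups are not affected. A patient who stops at the site on the day of Visit 4 still has that visit's assessments. A patient whose only accepted recordings fall outside the analysis windows stays in the FAS, because the FAS rule mentions no window.

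**Inputs (SAP 4.1, Protocol 9.2).** Placebo mean log10 ratio -0.160; planned difference -0.163; SD 0.371; 93 per arm. The active mean is taken as -0.160 + (-0.163) = -0.323.

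**Plan's own figure.** A two-sample t-test at two-sided 5% with difference 0.163, SD 0.371 and 83 per arm has 80.3% power. Then 83/0.90 = 92.2, rounded up to 93, and 4 × 93 = 372. The plan's sample size reproduces.

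**Adding the omitted patients.** Let k of 93 patients in an arm be imputed at baseline (log ratio 0), with p = k/93 and m the arm's planning mean.

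- Arm mean = m(1 - p)
- Arm variance = (1 - p) × 0.371² + p(1 - p) × m²
- Difference = -0.323(1 - p_active) + 0.160(1 - p_placebo)
- Reduction versus placebo = 1 - 10^difference

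Example with 5 active and 0 placebo: p = 0.0538; active mean = -0.323 × 0.9462 = -0.3056; difference = -0.3056 + 0.160 = -0.146, which is 11% smaller than -0.163. Active variance = 0.9462 × 0.1376 + 0.0538 × 0.9462 × 0.1043 = 0.1356, so the SD is 0.368.

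Power is from the noncentral t with Welch degrees of freedom, without covariate adjustment. The FAS comparator keeps difference -0.163 (reduction 31.3%) and SD 0.371 with 93 - k patients per arm, and assumes that every FAS patient has a Visit 6 value.

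| Omitted, active / placebo | All-dosed difference | Shift | Reduction v placebo | Power, all dosed | Power, FAS |
|---|---|---|---|---|---|
| 3 / 0 | -0.153 | 6% smaller | 29.6% | 80% | 84% |
| 5 / 0 | -0.146 | 11% smaller | 28.5% | 76% | 84% |
| 9.3 / 0 (10% v 0) | -0.131 | 20% smaller | 26.0% | 67% | 83% |
| 3 / 3 | -0.158 | 3% smaller | 30.5% | 83% | 83% |
| 9.3 / 9.3 (10% each) | -0.147 | 10% smaller | 28.7% | 79% | 81% |
| 2 / 9 | -0.172 | 5% larger | 32.6% | 89% | 82% |

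**Break-even.** The difference is unchanged when 0.323 × p_active = 0.160 × p_placebo, that is, when placebo loss is 0.323/0.160 = 2.02 times active loss. Below that ratio, equal loss included, the FAS-only result favours the dose. Above it, the all-dosed result does.

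**Robustness.** Using the observed proof-of-concept active mean of -0.327 in place of -0.323 changes the percentage shifts by less than one point.

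**The case against.** Four points can fairly be made for the plan.

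- **The group may be small.** SAP Appendix 2 sets no minimum recording length and the stated length-based rejection applies only under 1 hour, so a patient who stays on study must lack an accepted recording at Visits 4, 5 and 6 to be excluded. This stands: the gap is mainly loss in about the first week.
- **The larger scenarios have no support in the documents.** The 10% allowance is per group and for any reason, so it does not support a one-sided split. The proof-of-concept study had N = 31 on 150 mg and N = 30 on placebo, with no sign of excess loss on active drug. This also stands, although that study was a small crossover that tested only 150 mg.
- **The shift depends on the imputation.** Give early leavers the placebo mean of -0.160 instead of 0, and active-only loss of 3, 5 or 9.3 patients yields -0.163(1 - p) = -0.158, -0.154 or -0.147. These shifts of 3%, 5% and 10% are about half those tabulated, and placebo loss then has no effect. So the break-even ratio belongs to baseline-value imputation and not to early loss in general. But baseline-value imputation is the method that the SAP itself chose.
- **Reporting is already planned.** By-arm FAS counts, the listing of exclusions and the discontinuation tables would let a reader approximate the unadjusted shift by hand. That gives neither an adjusted estimate nor a confidence interval.

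These points limit the likely size. They do not put the omitted patients into any planned analysis of the primary endpoint.

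**Conclusion.** The concern holds. No planned analysis of the primary endpoint includes a dosed patient with a baseline but no accepted post-dose recording, and the baseline-value ANCOVA is the one planned missing-data analysis that could. The effect may be slight: 3 patients in each arm change the difference by 3% with power unchanged at 83%. It reaches 20% only if a tenth of one active arm and no placebo patients are affected, and it can run in either direction. All loss rates are assumptions, and the figures also rest on the planning means, an unadjusted comparison and complete Visit 6 data in the FAS. The primary analysis is unaffected. The change should be made because the gap falls on the patients whom a no-benefit analysis is meant to cover, in a trial that compares doses.

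**What to change.** In SAP 8.1.2, run the baseline-value ANCOVA on all randomised patients who took at least one dose and have an accepted baseline recording, analysed as randomised. Keep the FAS for the primary mixed model and for last-value imputation. Turn the planned by-arm counts and listing into one table of FAS exclusions by arm with reasons. Make the change before unblinding.

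The cost is one population change in the SAP and one more table, with no new data. The downside is a supportive estimate that may be less favourable. It assumes no change from baseline in patients never recorded on treatment, so it should be labelled as supportive only.
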